2.1 Purpose of the Study

The overall primary objective of the Pulse Glucocorticoid Therapy in Patients with ST-Segment Elevation Myocardial Infarction (STEMI) trial (PULSE-MI) is to test the hypothesis that administration of single-dose glucocorticoid pulse therapy in the *pre-hospital* setting reduces final infarct size in patients with STEMI treated with primary percutaneous coronary intervention (PCI).

2.2 Clinical Relevance

STEMI remains one of the leading causes of mortality globally despite significant advances in reperfusion therapies with timely primary PCI¹. One-year mortality following STEMI has decreased to around 10%, yet a substantial number of patients with STEMI develop heart failure (HF) (22%) which impairs prognosis significantly²⁻⁶. A main driver for mortality and heart failure following STEMI is infarct size that is the cause of ischemia and reperfusion injury⁷. Of note, inflammation is induced immediately after the onset of acute myocardial ischemia and is subsequently exacerbated following reperfusion⁸. Hence, inflammation in the setting of STEMI is an important factor in both acute myocardial ischemia and reperfusion injury, which is why inflammation *per se* is a feasible and desirable target for improving prognosis in these patients.

[figure not shown]

2.4 Glucocorticoids and STEMI

Glucocorticoids are crucial in regulation of the systemic inflammatory response and may therefore be beneficial in limiting myocardial injury following STEMI^{18, 19}. Glucocorticoids mediate two different mechanisms: the genomic effect mediated by glucocorticoid receptor occupation, gene transcription, and translation within the cells which is induced within hours and the non-genomic effect, which is induced rapidly (<15 minutes) after administration via plasma membrane bound receptors and independent of cytosolic receptor occupation and genomic regulation^{20, 21}. Some of the proposed nongenomic effects of glucocorticoids on the cardiovascular system include decreased vascular inflammation and reduced infarct size by activating the endothelial nitric oxide synthase (eNOS), cardioprotection through membrane stabilization through nitric oxide (NO) production, and increasing the contractility of the vascular smooth muscle cells²⁰. Taken altogether, the non-

genomic actions secure that the anti-inflammatory effect is initiated quickly to protect the myocardium immediately whereas, in addition, the genomic actions protect the tissue in the subsequent period. The use of glucocorticoid in relation to ischemia has therefore been investigated in experimental, in-vivo, and clinical studies in the 1970's and 1980's. In experimental animal studies, glucocorticoids showed beneficial effects on hemodynamics and infarct size following ischemia, however most studies were performed in non-reperfused animals^{16, 19, 22}. Albeit this, clinical studies in patients with AMI have shown conflicting results^{16, 19, 22}. Further, definitive conclusions on glucocorticoids' efficacy in patients with STEMI are difficult to draw due to different study designs, investigational agents, and medicine dosage¹⁶. However, most importantly, all studies performed in patients with AMI were before the era of primary PCI¹⁶, and since the implementation of PCI in treatment of STEMI, the prognosis in these patients has improved significantly¹. Considering these advances in reperfusion strategies, glucocorticoids may now add an additional beneficial role in limiting infarct size and improving prognosis in patients with STEMI¹⁹. Although questions have been raised of impaired infarct healing in relation to glucocorticoid treatment in the setting of STEMI, the concern is not supported by randomized controlled clinical trials^{16, 23}. Long-term use of glucocorticoids is, however, associated with adverse side-effects, but short-term use of glucocorticoids has only few side-effects²⁴. None of the previous studies have investigated single-dose pulse therapy with glucocorticoids in patients with STEMI who were treated with primary PCI. Based on reperfusion advances, role of inflammation in both STEMI and reperfusion injury, and few side effects of short-term use of glucocorticoid, intravenous short-term treatment with glucocorticoid could add potential benefit and have an important therapeutic role in limiting the degree of myocardial injury and thereby improving prognosis in patients with STEMI.

2.5 Safety and Rationale

In light of the above, we will investigate the well-known, widely used, and highly potent glucocorticoid, methylprednisolone, administered as single pulse-dose therapy prior to primary PCI in patients with STEMI in a randomized clinical trial.

Pulse glucocorticoid therapy was first used for acute rejection following kidney transplantation²⁵, and is defined as treatment with ≥ 250 mg prednisolone or equivalent for one or more days²⁶. Pulse glucocorticoid therapy is now used as effective and safe treatment of a wide range of diseases such as rheumatic diseases, dermatologic diseases, optic neuritis, multiple sclerosis, acute disseminated encephalomyelitis, glomerulonephritis, and systemic vasculitis²⁷. Doses up to 2500

mg methylprednisolone, depending on disease severity, are recommended and used in treating these inflammatory conditions²⁷. The beneficial acute effects of pulse glucocorticoid therapy in these conditions are thought to be mediated by the nongenomic effects of glucocorticoids via plasma membrane bound receptors, and the estimated complete glucocorticoid receptor occupation is reached at approximately 100 mg methylprednisolone, reaching maximum activation around 250 mg^{27, 28}. Genomic mechanisms cannot explain the beneficial effects of glucocorticoid doses >100 mg, and the extent of receptor activation is directly dependent on methylprednisolone dosage²⁹. Despite concern of serious adverse events (SAEs) following high-dose methylprednisolone, intravenous pulse therapy is not associated with increased risk of mortality, adverse events (AEs), or AEs leading to discontinuation of pulse methylprednisolone^{30, 31}. The Norwegian “Summary of Product Characteristics” (SPC) for Solu-Medrol (methylprednisolone) recommends doses up to 30 mg/kg. The Danish SPC for Solu-Medrol (methylprednisolone) recommends infusion of 250 mg methylprednisolone over a period of ≥ 5 minutes³². This is due to the potential side-effects of a rapid infusion of methylprednisolone. These potential side-effects are, however, not well supported by the literature. In fact, pulse glucocorticoid therapy administered intravenously over a short period of time has few side effects compared with long-term oral treatment^{24, 30, 33}. Considering this knowledge, safety, and potential beneficial dual effects in patients with STEMI undergoing primary PCI, administration of 250 mg methylprednisolone administered in the *pre-hospital* setting may well offer substantial advantages in these patients. The expected effect will then translate into reduced infarct size, better clinical outcomes including fewer patients with HF and subsequently reduced mortality following STEMI.

3. Hypothesis

In patients with STEMI undergoing primary PCI, 250 mg methylprednisolone administered in the *pre-hospital* setting limits reperfusion injury and reduce final infarct size measured by late gadolinium enhancement (LGE) on cardiac magnetic resonance (CMR) 3 months after STEMI.

4. Objectives of the Study

4.1 Overall Primary Objective

To determine whether 250 mg methylprednisolone administered in the *pre-hospital* setting reduces final infarct size on CMR in patients with STEMI undergoing primary PCI.

4.2 Secondary Objectives

- To determine whether the response of methylprednisolone differs in pre-specified sub-groups: age, gender, pre-PCI Thrombolysis in Myocardial Infarction (TIMI) flow, culprit in left anterior descending artery (LAD), time from first medical contact to primary PCI, and duration of symptoms prior to primary PCI.
- To determine whether methylprednisolone improves LVEF within 48 hours and 3 months after primary PCI.
- To determine whether methylprednisolone decreases acute infarct size and edema measured on CMR within 48 hours of primary PCI.
- To determine whether methylprednisolone decreases degree of microvascular obstruction (MVO) and hemorrhage measured on CMR within 48 hours of primary PCI.
- To determine whether methylprednisolone inhibits the inflammatory response at admission, 24 hours after admission and after 3 months. Markers of inflammation: High sensitivity C-reactive protein (hsCRP), leucocyte- and differential count, plasma cytokine levels (IL-1b, IL-2, IL-3, IL-4, IL-5, IL-6, IL-7, IL-8, IL-10, IL-12, IL-13, IL-17A, G-CSF, GM-CSF, MCP-1, MIP-1beta, INF-g and tumor-necrosis factor α (TNF- α)), and procalcitonin
- To determine whether methylprednisolone increases myocardial salvage index (MSI) on CMR
- To determine whether methylprednisolone increases coronary flow reserve (CFR) and decreases index of microcirculatory resistance (IMR).
- To determine whether methylprednisolone improves clinical outcomes (all-cause mortality and hospitalization for HF) at one year after primary PCI.
- To determine whether methylprednisolone decreases peak Troponin-T and creatine kinase myocardial band (CKMB) during admission.

All these outcomes are relevant to patients with STEMI and have the potential to change the clinical course following STEMI and standard clinical practice.

5. Endpoints and Follow-Up

Primary and secondary endpoints are listed in Table 1.

Table 1. PULSE-MI endpoints

	Intervention with glucocorticoid vs. no intervention	Timeframe
Primary endpoint	Final infarct size (% of ventricular mass) measured by LGE on CMR	3 months after primary PCI
Secondary endpoints	The extent of MVO on CMR	Within 48 hours after primary PCI
	The extent of hemorrhage on CMR	Within 48 hours after primary PCI
	Other CMR efficacy parameters as specified in the appendix A	Within 48 hours and 3 months after primary PCI
	All-cause mortality and hospitalization for HF	3 months after primary PCI
	Peak Troponin-T and CKMB	During admission
	Safety: Incidence of adverse events the first seven days of index event	Within 7 days of STEMI

Exploratory endpoints:

1. Pre-PCI and post-PCI TIMI flow
2. C-reactive protein (CRP), leucocyte- and differential count, thrombocytes, HbA1c, p-Glucose, pro-brain natriuretic peptide (BNP), creatine kinase, creatinine, potassium, and sodium at admission, during admission and after 3 months
3. Arrhythmia (ventricular tachycardia/ventricular fibrillation) during transportation in the ambulance and peri-procedural during PCI
4. Bolus CFR, IMR, absolute CFR, and microvascular resistance reserve (MRR) following primary PCI
5. LVEF on transthoracic echocardiography during admission and one to three months following primary PCI
6. Killip Class at admission

7. Biomarkers of inflammation at admission, 24 hours after admission, and after 3 months
8. All-cause mortality and hospitalization for HF after 1 and 10 years

5.1 Endpoint Definition

All clinical endpoints (all-cause mortality and hospitalization for HF) are defined in Appendix B. The CMR efficacy parameters are described in Appendix A. Secondary endpoints will be identified using hospital files in which all deaths and hospital referrals are reported.

Events will subsequently be adjudicated by members of our clinical events committee (CEC), who will review all relevant medical records.

5.2 Event Recording

Violations of the protocol will be monitored continuously. The CEC is responsible for adjudicating the clinical secondary endpoints. No members of the CEC participate in recruitment or data collection or have access to any information regarding treatment allocation. A list of all CEC members is given in Appendix C.

5.3 Monitoring

Monitoring of the study will be done by a local Good Clinical Practice (GCP) unit. The trial will be conducted in compliance with the published trial protocol, the Helsinki Declaration, the GCP guidelines (ICH-GCP), and national laws. The Sponsor of the trial allows investigators and institutions involved in the trial to perform trial-related monitoring, audit, and inspection from the authorities including direct access to the data and documents related to the trial.

The first monitoring meeting will be held after inclusion of 2 patients. The following meetings will be held as needed. A full monitoring plan will be elaborated and composed before initiation of the study by the local GCP unit.

6. Study Setup

6.1 Study Design

This study is an investigator-initiated, 1:1 randomized, double-blinded, placebo-controlled prospective clinical proof-of-concept trial to investigate whether pulse therapy with 250 mg methylprednisolone in the *pre-hospital* setting limit reperfusion injury and reduce infarct size, and subsequently improve clinical outcomes in patients with STEMI undergoing primary PCI. The trial will be

[figure not shown]
chaired at the Department of Cardiology, Rigshospitalet, Copenhagen University Hospital, Denmark.

6.2 Target Patient Population and Number of Patients

The target patient population is male and female patients aged 18 years and over with documented evidence of STEMI, eligible planned for primary PCI who had symptom onset within 12 hours before randomization who were initially managed by an ambulance paramedic and included by the referring and including doctor (on-call cardiology fellow doctor (RD) at Rigshospitalet) in the *pre-hospital* setting.

A total of 378 patients with STEMI (189 patients treated with intravenous infusion of 250 mg methylprednisolone and 189 patients with intravenous placebo infusion) are included for the primary endpoint of final infarct size (% LGE of the LV) on CMR at 3 months. The inclusion will continue until this number has been reached and with an expected drop-out rate of 40%, 530 patients need to be included and randomized. All patients will be included in the *pre-hospital* setting from throughout the Capital Region and Region Zealand of Denmark (Figure 2).

Figure 2. Flowchart of the study

[figure not shown]
6.3 Study Setting

In all, patients with STEMI will be included in the *pre-hospital* setting throughout the Capital Region and Region Zealand of Denmark prior to primary PCI at Rigshospitalet, Copenhagen University Hospital, Denmark if eligible to participate in the study. Eligibility will be carefully screened by the RD at Rigshospitalet. Data collection and analysis will be undertaken through the Department of Cardiology, Rigshospitalet, Copenhagen University Hospital, Copenhagen, Denmark.

6.4 Estimated Study Duration

We expect the study to begin once the study has been approved by the government. Rigshospitalet performs approximately 1000 primary PCI procedures per year³⁴. An inclusion is planned to be completed in 36 months, and the 3-months follow-up period will be completed after 39 months. However, the study will be stopped before when 378 patients have completed CMR at 3 months. Following completion of the trial, the hospital records will be accessed at 1 and 10 years to obtain information on mortality and hospitalization for HF (Figure 3).

Figure 3. Timeline of the study

6.5 Inclusion and Exclusion Criteria

Inclusion criteria for recruitment are listed below and must be fulfilled for the patient to be randomized:

1. Age ≥ 18 years including fertile women*.
2. Acute onset of chest pain with < 12 hours duration.
3. STEMI as characterized on electrocardiogram (ECG) by one of the following:
 - 1) at least two contiguous leads with ST-segment elevation ≥ 2.5 mm in men < 40 years, ≥ 2 mm in men ≥ 40 years, or ≥ 1.5 mm in women in leads V_2 - V_3 and/or ≥ 1 mm in the other leads,
 - 2) presumed new left bundle branch block with ≥ 1 mm concordant ST-segment elevation in leads with a positive QRS complex, or concordant ST-segment depression ≥ 1 mm in V_1 - V_3 , or discordant ST-segment elevation ≥ 5 mm in leads with a negative QRS complex,
 - 3) Isolated ST depression ≥ 0.5 mm in leads V_1 - V_3 and ST-segment elevation (≥ 0.5 mm) in posterior chest wall leads V_7 - V_9 indicating posterior acute myocardial infarction (AMI),
 - 4) ST-segment depression ≥ 1 mm in eight or more surface leads, coupled with ST-segment elevation in aVR and/or V_1 suggesting left main-, or left main equivalent-coronary obstruction.

Exclusion criteria for recruitment are listed below and none of the criteria must be fulfilled for a patient to be eligible:

1. Presentation with cardiac arrest (out of hospital cardiac arrest (OHCA)).
2. Time from symptoms onset to primary PCI > 12 hours.
3. Known allergy to glucocorticoid or known mental illness with maniac or psychotic episodes.

* It is not possible to perform a pregnancy test (HCG urine test) in the pre-hospital setting. However, methylprednisolone is not contraindicated in pregnant women.

4. Patients with previous AMI in the assumed culprit artery.
5. Previous coronary artery bypass graft (CABG).
6. Unable to read and understand Danish.

7. Ethical Assessment

The patient will be informed and treated according to the international guidelines (ICH-GCP) and protected under the General Data Protection Regulation (GDPR) including the processing of personal data (data protection law) and the Danish Health Act. As to the need for fast transportation and treatment (primary PCI), the main ethical issue that could arise from this trial is that informed consent cannot be obtained prior to intervention and treatment with primary PCI due to the acute setting of the study. Intervention before informed consent is done to secure initiation of the study treatment as soon as possible due to the need of acute intervention and treatment in STEMI and vulnerable patients. Moreover, the ability of the patient to provide informed consent in the *pre-hospital* setting is questionable due to vulnerability, chest pain and acute setting. This implies the following:

- Recruitment and randomization in the *pre-hospital* setting will be performed by the paramedic in the ambulance.
- The including doctor is the RD at Rigshospitalet. The including RD is continuously in touch with the paramedic in the ambulance by telephone from the time of screening until randomization has been done.
- The patient will provide informed consent as soon as possible following the acute management of the patient (primary PCI), once the patient is stable.
- The process of informed consent is described thorough in section 9.2. The process follows article 35 of Clinical Trial Regulation EU No 536/2014 and Law of Clinical Trials, §3.
- The justification for providing informed consent following intervention due to the emergency situation is described thorough in the section 9.2.1.

8. Study Progress and Conduct

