8.3 Randomization

Randomization of the patient will take place in the *pre-hospital* setting. Patients who satisfy all the eligibility requirements will be randomized. Randomization is done by the paramedic in the ambulance. Patients will be randomized in a 1:1 ratio to either infusion of 250 mg methylprednisolone or placebo that are placed in identical boxes. The paramedic randomizes the patient by picking a random box stored in the ambulance delivered by the pharmacy, including methylprednisolone or placebo, and administers (over a period of 5 minutes) the content by a bolus infusion. Following infusion of the randomized treatment, the ambulance will bring the box to the hospital alongside with ECGs obtained in the ambulance in case of emergency unblinding. All boxes are identical and has a unique box serial number. Once a patient has been randomized, the patient is considered enrolled and included in the study. The box serial number is not necessarily the same as the patient identification number. In case of any technical issues, the responsible Ph.D. student or other investigators from the steering committee will be available.

All including RD's at Rigshospitalet, legally designated representative, and paramedics have relevant knowledge of the study from the handing out of the study protocol, protocol summaries, and pocket cards as well as via e-mail and on-going project recaps. None of the including RDs, legally designated representative, or paramedics are involved with the trial except for screening, enrollment, and inclusion of the patients.

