8.9 Concomitant Procedures

8.9.1 Primary PCI Procedure

The patient is admitted to the hospital because of STEMI with symptom onset less than 12 hours before contact, defined as a primary PCI according to guidelines¹⁰. The primary PCI will be performed as usual clinical practice. The patient is pretreated with aspirin (300 mg) and 10.000 units of heparin in the *pre-hospital* setting by the paramedics as soon as the including RD at Rigshospitalet has set the diagnosis of STEMI and referred the patient to primary PCI at Rigshospitalet, Denmark. These procedures are of standard clinical practice and in accordance with guidelines. Primary PCI is prepared and performed as usual in the catheterization laboratory. Immediately subsequent to primary PCI, a loading dose of either 60 mg prasugrel or 180 mg ticagrelor is given per os. Clopidogrel 600 mg can be chosen alternatively at the discretion of the treating physician (e.g. high bleeding risk, ongoing anticoagulation therapy).

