### Statistical Analysis

Due to the inclusion and randomization in the prehospital setting, post-randomization exclusions of patients who do not fulfill criteria is expected. The post-randomization exclusions will include patients who are not eligible or patients with other reasons for ST-segment elevation. A differentiation between a classic type 1 acute myocardial infarction with plaque rupture and thrombosis formation and a type 2 acute myocardial infarction with other reasons for ST-segment elevation (e.g. takotsubo, myocarditis, pericarditis, spontaneous coronary artery dissection, coronary embolism, coronary spasm, anemia, etc.) can only be made after further evaluation including initial coronary angiogram and thus after inclusion. Patients included and subsequently excluded will not be included in the modified intention-to-treat population. The modified intention-to-treat population is prespecified and will not be changed during the trial.

Analyses for the primary and secondary outcomes will be performed in the modified intention-to-treat population. Thus, safety including adverse events and serious adverse events and reactions will be assessed in all randomized patients which will be included in the Supplemental Material. Safety in all randomized patients will be further analyzed by calculating a cumulative incidence curve of all-cause mortality at three months which will be included in the Supplemental Material.

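### Exclusion 2 counts the 12-hour limit to primary PCI, after randomisation and infusion, so read literally a later delay can drop a patient who was eligible at randomisation from the mITT set

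*Protocol*

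**What the plan says.** The protocol states the 12-hour limit in four ways:

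- **6.2, target population:** patients "who had symptom onset within 12 hours before randomization".
- **6.5, inclusion 2:** "Acute onset of chest pain with < 12 hours duration", with no statement of when the duration is read.
- **6.5, exclusion 2:** "Time from symptoms onset to primary PCI > 12 hours".
- **8.9.1, description of the PCI procedure:** "symptom onset less than 12 hours before contact".

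On sequence, section 8.3 says: "Randomization of the patient will take place in the *pre-hospital* setting". It adds: "Once a patient has been randomized, the patient is considered enrolled and included in the study". Section 8.4 has the infusion given over 5 minutes during transport, so both steps come before PCI.

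On consequences, protocol 8.7 excludes randomised patients who do not meet the criteria and keeps them for 3 months of safety follow-up. Section 10.2 treats them as screen failures and compares only patients who meet every criterion. The SAP (Statistical Analysis) says: "The post-randomization exclusions will include patients who are not eligible or patients with other reasons for ST-segment elevation". It leaves these patients out of the mITT population, in which the primary and secondary outcomes are analysed.

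**The concern.** An eligibility criterion should be decidable when the patient is randomised. The actual time to PCI is not: it comes into being after the box is opened and the drug or placebo has been given. If it can decide who belongs to the efficacy population, membership depends on something that happens after treatment starts.

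This differs from the case the SAP argues for. The SAP justifies post-randomisation exclusion because the cause of ST elevation can be settled only after angiography. Takotsubo or myocarditis was already present at randomisation and is merely discovered later. A delay arises afterwards.

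The protocol's own premises leave room for a link with treatment. Section 2.4 expects non-genomic effects in under 15 minutes. Section 5 lists arrhythmia in the ambulance as an exploratory endpoint. Section 8.5 says the treating paramedic is unblinded after inclusion, and that the sponsor and investigators hold an allocation list. No blinded review of post-randomisation exclusions is described; under 5.2 the clinical events committee adjudicates clinical endpoints. Duration from symptoms to PCI is also a pre-specified subgroup factor (10.3), and the literal reading would truncate it after randomisation.

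**Working it through.** **1. The plan's own figure.** Inputs from protocol 10.1: mean 13%, SD 9%, relative reduction 20%, two-sided alpha 0.05, power 80%. The target difference is 0.20 × 13 = 2.6 points. Per arm, n = 2 × 9² × (1.960 + 0.842)² / 2.6² = 188.1, rounded up to 189. The total is 378, as stated, with power 0.802. The point below does not depend on this figure.

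**2. Where each clock stops.**

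| Place | Clock stops at | Known at randomisation? |
|---|---|---|
| 6.2 | randomisation | yes |
| 6.5, inclusion 2 | not stated; must be met to be randomised | yes, if read then |
| 8.9.1 | contact | yes |
| 6.5, exclusion 2 | primary PCI | no |

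**3. Following one patient through.** Take a patient randomised 11.5 hours after onset. The 6.2 limit and inclusion 2 are met. If PCI starts more than 12 − 11.5 = 0.5 hours later, exclusion 2 is met on its literal wording. Sections 8.7 and 10.2 and the SAP then take the patient out of the efficacy comparison. None of the three confines exclusion to facts fixed before randomisation.

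**4. How many.** The documents give no share. If 1% to 5% of the 530 planned patients crossed 12 hours between randomisation and PCI (an assumption), that is 0.01 × 530 = 5.3 to 0.05 × 530 = 26.5 patients. Only those randomised shortly before 12 hours are at risk, and section 9.2.1 says most transports take under 30 minutes.

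**5. How much bias, in an unfavourable case.** Suppose a fraction f is removed from one arm only, and those patients have a mean infarct size e points above the arm mean of 13%. The mean of the remaining patients is (13 − f(13 + e)) / (1 − f), a fall of f × e / (1 − f).

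- f = 0.01, e = 5: 0.05 / 0.99 = 0.05 points, or 2% of 2.6.
- f = 0.05, e = 10: 0.50 / 0.95 = 0.53 points, or 20% of 2.6.

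The values of f and e and the one-sided removal are all assumptions. Equal removal from both arms would cause little bias.

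**6. Power.** Without replacement, losing 5% of 378 would leave about 359 patients and power of 0.781 against 0.802. Accrual continues until 378 complete the CMR (10.1 and SAP, Sample Size), so even this loss is largely avoided.

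**The case against.** The best defence is that exclusion 2 is a screening judgement. It stands in a list of criteria for recruitment. Section 6.2 speaks of patients planned for primary PCI, and section 8.1 has the referring doctor check eligibility by telephone before the patient is included. With short transports, that doctor can estimate whether PCI will fall within 12 hours. This may well be what was meant. However, the text does not say expected time, and 8.7, 10.2 and the SAP allow the other reading.

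It is also fair that 8.9.1 describes a procedure and 6.2 summarises a population, so the conflict that matters most is within 6.5. And the SAP refers to a published plan, not among these documents, which may limit the exclusions.

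A reader might go further and infer that the plan intends to drop late-PCI patients, that the randomised comparison is therefore broken in a group with large infarcts, and that power suffers. The documents do not support this. The SAP's reason for exclusion is diagnostic and does not mention delay. Section 8.4 says the study medicine will not prolong transport or any aspect of standard treatment, and under 8.5 the unblinded paramedic takes no further part after arrival. No infarct size by delay is given. Safety is still assessed in all randomised patients.

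**Conclusion.** The point holds as a defect in the rules as written. One of four 12-hour statements ends after treatment, and nothing stops it from removing a randomised patient from the mITT set. The SAP's diagnostic rationale does not cover a delay that arises after randomisation, so this is more than a missing detail.

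The expected effect is modest. The 5 to 27 patients (5.3 to 26.5, rounded) rest on an assumed 1% to 5%. The shift of 2% to 20% of the target difference also assumes removal from one arm only and infarcts 5 to 10 points larger. Removal that differs by arm or is related to treatment is possible but not shown. The change is worth making because it costs almost nothing and closes a route to bias.

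**What to change.** 1. **Protocol:** reconcile 6.2, both criteria in 6.5, and 8.9.1, so that the 12-hour limit has one stated endpoint, and say whether any PCI-based wording means actual or expected time. Which clinical limit is right is for the sponsor; this review does not choose one.
2. **SAP:** state that eligibility for the mITT set is judged only on facts fixed at or before randomisation, including those discovered later, such as an alternative diagnosis. Actual time to PCI then does not remove a patient from the set. Section 8.2 already records the time of intervention, which helps to apply the rule.
3. **Reporting:** give onset-to-PCI time descriptively by arm.

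The cost is wording in two documents. The downside is that a few late-PCI patients stay in the efficacy analysis.
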